15.3 Sample size

Up to 70 healthy female volunteers will be included in part A (7 cohorts of 10 volunteers) and up to 240 in part B (3 cohorts of 80 volunteers). The final number of volunteers to be randomized in part B will be calculated following a data review from part A.

15.4 Studied criteria for the two study parts

15.4.1 Characteristics of included volunteers

- **Volunteer demographic characteristics**

For demography, continuous variables (for example: age, height, weight, BMI) and qualitative variables (for example: ethnical origin) will be summarised using descriptive statistics on all included volunteers. Demographic characteristics will be also presented for other study populations (IG and/or PP) if they are different from ITT.

- **Medical history events**

Medical and surgical history events will summarised by System Organ Class (SOC) and Preferred Term (PT). In case of few relevant history events (≤ 5 per study part for example), only a listing will be provided according to treatment/dose group and volunteer.

- **Physical examination**

Abnormal physical findings at screening period or at V2 pre-dose (study baseline) will be listed by treatment/dose group, volunteer and visit.

- **Pregnancy test**

If applicable, serum pregnancy test will be performed at screening and post-study medical visit and urine pregnancy test will be performed prior each administered dose (primary and booster doses at V2 and V6 respectively) and only for part B at V10. If no booster dose is administered then no pregnancy test will be scheduled at V6. A listing of positive results will be presented by treatment/dose group, volunteer and visit.

- **Previous medications**

[REDACTED]
[REDACTED] a listing will be presented by treatment/dose group and volunteer.

- **Concomitant medication**

[REDACTED]
[REDACTED] volunteers who received concomitant treatments along with the study conduct (including emergent and non-emergent treatments) will be listed by treatment/dose group.

If relevant, frequency of volunteers taking concomitant medications and occurrence number of each medication will be summarised by Anatomic and Therapeutic Class (ATC) and Preferred Term (PT) for each treatment/dose group.

15.4.2 Primary endpoint for the two study parts

The primary objective is to evaluate the safety and tolerability of the GBS-NN vaccine for 12 weeks after the first dose of vaccine.

All the included volunteers (including the withdrawal and dropout volunteers) will be evaluated for safety analysis (ITT).

The following endpoints will be evaluated:

- **Local and systemic reactogenicity**

Assessment results will be described according to treatment/dose group and visit.

- **Adverse events**

Adverse events will be coded according to the Medical Dictionary for Regulatory Activity (MedDRA). They will be classified into pre-defined standard categories according to chronological criteria:

- Treatment Emergent Adverse Events (TEAEs): AEs which occur for the first time after the first administration or present before and worsened during vaccine exposure;
- Non-Treatment Emergent Adverse Events (NTEAEs): AEs which occur before the first study vaccine administration (also called "pre-dose event").

TEAEs will be described by relation to study vaccine (for example: definite / probable / possible / unlikely / unrelated) and maximum intensity (for example: mild / moderate / severe) according to treatment/dose group. Descriptive statistics will be characterised by number of TEAEs, number and percentage of volunteers with at least one TEAE (based on ITT). In case of few TEAEs (≤ 5 per study part for example), only a listing will be performed.

Vaccine related TEAEs (*i.e.* definite, probable or possible relationship to study vaccine) will be summarised by MedDRA codes (SOC and PT) and treatment/dose group. In case of few vaccine related TEAEs (≤ 5 per study part for example), only a listing will be performed. TEAEs not related to study vaccine (*i.e.* unlikely or unrelated relationship to study vaccine) will also be summarized by MedDRA codes.

Two distinct listings of TEAEs and NTEAEs will be presented by treatment/dose group, volunteer and MedDRA codes in order to provide more information about adverse events (example: description, duration, time since last administration if applicable, seriousness, any actions taken as concomitant medication or hospitalization).

- **Laboratory tests**

Biochemistry and haematology tests will be performed at V1 (screening), V4 (part A), V5 (part B), V8 (parts A and B) and post-study medical visit (V10 for part A and V20 for part B).

Parameter values, position according to laboratory ranges (if available) and investigator assessment will be described according to visit for each treatment/dose group. In order to study evolution of parameters after vaccination, parameter values changes from pre- to post-dose visits will be performed. Emergent values (for parameters with available laboratory ranges) with their corresponding position according to ranges will be listed by treatment/dose group and volunteer.

- **Urinalysis**

Urinalysis will be performed at V1 (screening), V4 (part A), V5 (part B), V8 (parts A and B) and post-study medical visit (V10 for part A and V20 for part B).

Parameter values (quantitative or binary results, *i.e.* positive/negative), position according to laboratory ranges (if available) and investigator assessment will be described according to visit for each treatment/dose group. In order to study evolution of continuous parameters after vaccination, parameter values changes from screening to post-study medical visit will be performed. Emergent values (for parameters with available laboratory ranges or with binary results) will be listed by treatment/dose group and volunteer.

- **Vital signs**

Vital signs will be characterised by heart rate, blood pressure, tympanic temperature and respiratory rate. Vital signs will be assessed at V1 (screening), V2 (pre-dose, T2h and T3h post-dose), V3, V4 (part A only), V6 (pre-dose and T2h post-dose for volunteers receiving booster dose), V7 (only if administered booster dose), V8, and post-study medical visit (V10 for part A and V20 for part B). For study part B, additional vital signs assessments will be performed at V5, V8, V9, V10, V11, V13, V15 and V17.

Parameter values, position according to reference ranges (if available) and investigator assessment will be described according to visit and assessment time for each treatment/dose group. In order to study evolution of parameters after vaccination, parameter values changes from pre-dose to post-dose assessments will be performed. Emergent values (for parameters with available reference ranges) with their corresponding position according to reference ranges will be listed by treatment/dose group and volunteer.

- **12-lead ECG parameters**

ECG will be assessed at V1 (screening) and post-study medical visit (V10 for part A and V20 for part B).

Parameter values, position according to reference ranges and investigator assessment (if available) will be described according to visit for each treatment/dose group. In order to study evolution of parameters after vaccination, parameter values changes from screening to post-study medical visit will be performed. Emergent values (for parameters with available reference ranges) with their corresponding position according to reference ranges will be listed by treatment/dose group and volunteer.

- **Physical examination**

Abnormal physical examinations recorded at post-study medical visit (V10 for part A and V20 for part B) will be listed according to treatment/dose group and volunteer.

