Visit 9 will be performed 8 weeks following the first study vaccine administration and the following assessments will be performed: an assessment of the injection site and a pharmacodynamic blood sample will be taken to measure antibody response and AEs and concomitant medications will be reviewed.

Post-Study Medical (Visit 10)

A post-study medical will be performed 12 weeks following the first study vaccine administration and the following assessments will be carried out: an assessment of the injection site, a pharmacodynamic blood sample will be taken to measure antibody response, physical examination, vital signs, 12-lead ECG, urinalysis, blood samples for haematology and biochemistry, serum pregnancy test (if applicable) and a review of AEs and concomitant medications.

Safety Follow-Up (Visit 11)

A safety follow-up phone call will be performed 3 months after the end of the study (Visit 10) i.e. 6 months following the first study vaccine administration to check the general health of the volunteer and to review significant AEs.

[REDACTED]

In both Part A and Part B, following the primary dose volunteers will remain in the study unit for 8 hours post-dose to ensure that no significant AEs occur and the medicinal product is well tolerated. No additional acute safety concerns are considered likely to occur following 8 hours of observation. Following the booster dose volunteers will remain

in the clinic for at least 4 hours post-dose, as the volunteer has tolerated the initial dose, and therefore, tolerability should be consistent. The concern is for an acute systemic reaction following the booster dose. It is not considered necessary to keep the volunteers in the study unit overnight as no samples are being taken and the time intervals are considered appropriate to assess the safety and tolerability prior to discharge.

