12.6 Individual Volunteer Stopping Criteria

Volunteers who meet one or more of the following stopping criteria will receive no further doses of study vaccine but will be followed up for safety:

- Severe injection site reaction, see Appendix 1
- Severe systemic reaction, e.g. anaphylaxis, see section 14.2.1
- Persistent febrile reaction (>38.9°C and >24 hours) at the Investigator's discretion
- SAE related to the study agent

The medical safety of the volunteer is of paramount importance when discussing study continuation.

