15.1 Statistical method description

15.1.1 General information

Statistical results will be separately presented for parts A and B.

Demographic, baseline characteristics and data recorded during the study will be summarised using descriptive statistics by treatment (placebo, vaccine taken alone or vaccine combined with adjuvant) and dose group, unless otherwise specified. If relevant additional descriptive graphs can be provided.

Individual data for all included volunteers will be presented as a data listing, sorted by treatment and administered dose level.

For parameters with evaluation before vaccination and in case of re-checked value(s), only the last observation prior to dosing will be used in descriptive and inferential statistics and derivations of other parameter values. After vaccination, only values of scheduled assessments (planned in the protocol) will be used.

For laboratory/clinical parameters for which laboratory/reference ranges will be available, position of parameter values according to ranges will be flagged with the following rule:

- "L" for values lower than laboratory/reference ranges;
- "H" for values higher than laboratory/reference ranges.

In addition, parameter values can be assessed by investigator and flagged as follows in order to determine clinical relevance:

- Normal;
- Abnormal and NCS (Not clinically Significant);
- Abnormal and CS (Clinically Significant).

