15.2 Studied populations for each study part

The following populations will be taken into account for each study part:

- **Intention to Treat Set (ITT):** All included volunteers who receive at least one dose of the study vaccine will be taken into account in the description of the population (disposition, demographic or baseline characteristics);
- **Immunogenicity Set (IG):** The subset of volunteers who will receive at least one dose of the study vaccine with available pre- and post-vaccination titers.
- **Per Protocol Set (PP):** All volunteers who receive both doses of the study vaccine and provide evaluable samples for analysis of the primary immunological endpoint and do not violate the protocol.

The Primary and Secondary Safety analyses will be performed on the ITT set. The Secondary Immunological analyses will be performed on the IG set. The “primary” immunological analysis (i.e. the results on Day 85 in both study parts) will also be performed on the PP set.

Missing or incomplete data will not be replaced, unless otherwise specified (example: values strictly under the LLOQ for immunogenicity data).

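### Section 15.4.2 pools treatment-emergent adverse events over both doses, so it specifies no TEAE rate by dose, although the protocol singles out systemic reactions after the booster

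*Combined protocol and SAP*

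**What the plan says.** Section 15.4.2 defines TEAEs as "AEs which occur for the first time after the first administration or present before and worsened during vaccine exposure". It describes them by relationship to vaccine, maximum intensity, MedDRA class and term, and treatment/dose group. The statistics are the number of events and the "number and percentage of volunteers with at least one TEAE (based on ITT". Section 15.2 defines the ITT set as "All included volunteers who receive at least one dose of the study vaccine". The default grouping in section 15.1.1 is "by treatment (placebo, vaccine taken alone or vaccine combined with adjuvant) and dose group, unless otherwise specified". Dose group there means dose level, not first or second injection.

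All six defined Part A cohorts are scheduled for two injections, on Days 1 and 29. Section 10.1 anticipates two doses in Part B but allows for one. On the time spent in the unit after the second injection, section 12.2.1 says "The concern is for an acute systemic reaction following the booster dose". It supports that arrangement with the statement "as the volunteer has tolerated the initial dose, and therefore, tolerability should be consistent".

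Other safety data are treated differently. For local and systemic reactogenicity, section 15.4.2 says "Assessment results will be described according to treatment/dose group and visit". Vital signs are to be described by visit and assessment time, including 2 hours after the booster at Visit 6, and Visit 7. The TEAE listing gives time since the last administration as an example item.

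**The concern.** Whether the second dose is tolerated like the first belongs to the primary safety objective. It also matters for choosing between one-dose and two-dose regimens. The protocol makes a statement about it and names the reaction it has in mind. The TEAE tables cannot examine that statement, because events after the two injections fall into the same cell.

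The by-visit reactogenicity summary would be the natural substitute, but nothing in the supplied text says how systemic symptoms enter it. If they are recorded as adverse events, their link to a particular dose survives only in a line listing, which gives no rate.

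**Working it through.** The plan gives no expected TEAE rate, power or alpha for safety, so there is no planned figure to reproduce. The check has three parts.

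**1. Where a systemic symptom after the booster would be recorded.**
- Appendix 1 grades the injection site only: redness, bruising, induration, itching, pain and other local reactions.
- Neither schedule in section 18 has a row for systemic reactogenicity.
- The visit descriptions in sections 12.2.1 and 12.2.2 list injection site, vital signs, laboratory tests and AE review, but no solicited systemic symptoms.
- Diary cards start only after Visit 10 in Part B.
- Section 12.6 refers severe systemic reactions to section 14.2.1, the AE intensity scale.

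Section 6.3 anticipates fatigue, malaise, myalgia and headache. On this text they are captured mainly as adverse events. Temperature is the exception, through vital signs.

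**2. What the pooled table can show.** Let p1 be the proportion of women with a TEAE after dose 1, p2 the proportion after dose 2, and j the proportion with both. If all are boosted:

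proportion with at least one TEAE = p1 + p2 − j

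With independent doses, j = p1 × p2, and this equals 1 − (1 − p1)(1 − p2). The rates below are assumptions.
- 30% then 10%: 1 − 0.70 × 0.90 = 0.37.
- 10% then 30%: 1 − 0.90 × 0.70 = 0.37.
- 5% then 15%: 1 − 0.95 × 0.85 = 0.1925. The reverse order gives the same value.

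In the first pair the booster rate differs three-fold and the entry is identical. Independence fixes the value of 37% but not the equality. For rates of 30% and 10%, j can run from 0 to 0.10, so the entry runs from 0.30 + 0.10 − 0 = 0.40 down to 0.30 + 0.10 − 0.10 = 0.30. For a given overlap it is the same in either order. The event count does not help: with 60 women and one event per reaction, the expected number is 60 × 0.30 + 60 × 0.10 = 24 either way.

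**3. What a fair comparison of doses needs.**
- *Windows.* Day 1 to Day 29 is 28 days and Day 29 to Day 85 is 56 days, so whole periods are not comparable. A 14-day window fits the AE reviews at Day 15 (15 − 1 = 14) and Day 43 (43 − 29 = 14) in both parts. The Day 8 contact has no counterpart after the booster, so ascertainment is somewhat closer after dose 1.
- *Women compared.* Under section 12.6, women who meet a stopping criterion "will receive no further doses of study vaccine but will be followed up for safety". They count after dose 1 but are not at risk after dose 2. Illustration, with assumed counts: 18 of 60 react to dose 1 (30%), and 3 of those 18 are not boosted. Among the 57 boosted, the dose 1 rate is 15/57 = 26.3%. If 15 of the 57 then react to dose 2, setting 26.3% against 30% looks like an improvement, although the rate in the same women has not changed.

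**The case against.** A reader might infer that a systemic reaction after the booster never gets a rate of its own, or that the safety analysis cannot show a worse booster. The documents do not support that. Systemic reactogenicity is named in the by-visit description, and the synopsis lists it, with scale variables, apart from adverse events. Visit 7 takes place only if a booster is given, so a summary at that visit covers boosted women. Vital signs, including temperature, are reported at set times after the booster, and laboratory results at Visit 8.

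A reader might also infer that the ITT denominator dilutes a post-booster rate. The plan tabulates no such rate for TEAEs, so there is nothing to dilute. The loss is dose attribution.

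The sentence about the booster explains observation time and is not an analysis objective. Moreover, section 12.2.1 describes different stays after the two doses for both parts, whereas section 12.2.2 gives the same minimum stay after each dose in Part B. Those passages must be reconciled, and the point here does not depend on which one applies.

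Finally, section 15 leaves detail to a SAP, and the supplied text contains no separate SAP. A by-dose table there cannot be excluded.

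These objections narrow the point to the TEAE tables but do not remove it. A by-visit summary is of little use for symptoms with no defined means of collection. Section 15.4.2 also specifies visit splits for reactogenicity, laboratory tests and vital signs, and none for TEAEs.

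**Conclusion.** The point holds for TEAEs. As written, their tables pool both doses, and no TEAE rate by dose is specified. Other outputs separate the booster in part, but for systemic symptoms that separation rests on an instrument the supplied text does not define.

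The size depends on rates the documents do not give. The 37% example shows that opposite patterns can be indistinguishable; it does not predict what this trial would find. The conclusion assumes that no systemic reactogenicity form and no by-dose TEAE table exist in documents that were not supplied. If either exists, the point shrinks or falls away. It does not arise for single-dose regimens. This is a cheap improvement to the primary safety analysis, not a fault that undermines it.

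**What to change.** For two-dose regimens, keep the overall ITT table in section 15.4.2. Add, by treatment/dose group, TEAEs and related TEAEs with maximum intensity, by onset within the same window after each dose (for example 14 days):

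- dose 1, among all dosed women;
- dose 2, among women who received the booster;
- dose 1 again, restricted to women who received the booster, so that the two doses are compared in the same women.

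State whether a symptom that recurs after the booster counts as a dose 2 event, since the TEAE definition speaks of first occurrence. Add a footnote that the Day 8 contact has no equivalent after the booster.

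The cost is extra output only. It needs dosing dates and AE onset dates, and changes no data collection, dose or clinical rule.

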The normal adverse event profiles from Phase I studies suggest that a typical array of minor clinical study symptoms may be experienced by volunteers taking part in the study. GBS-NN has not previously been tested in human volunteers, although it is known that naturally occurring antibodies, reactive against the GBS-NN are found in pregnant women; the possibility of as yet unknown side effects should remain a consideration. The protocol requires that volunteers are monitored after vaccine administration (vital signs and general signs and symptoms), with regular follow-up visits for physician assessment and questioning regarding AEs will be conducted for all volunteers in the study. GBS-NN, like other protein-based vaccines, may theoretically be associated with a transient febrile reaction (body temperature greater than 38.0°C but not greater than 38.7°C) following vaccination. Immune complex-mediated reactions are unlikely given the recombinant nature of GBS-NN, however, it is still possible that hypersensitivity may occur.

Based on the results from clinical use of other protein vaccines adsorbed to Alhydrogel®, and other aluminium containing adjuvants transient local reactions at the injection site, including pain, oedema, bruising, erythema and induration, mainly of mild intensity, are likely to occur. In addition flu-like symptoms, such as fatigue, malaise, myalgia, and mild to moderate headache may occur.

GBS-NN vaccination is contraindicated in volunteers known to suffer hypersensitivity reactions to vaccines or a known allergy to aluminium hydroxide. For the purpose of the study volunteers who have experienced a significant illness in the four weeks prior to check in will be excluded. The vaccine should not be given to volunteers with known or suspected immune deficiency, autoimmune diseases or who have an acute infection.

GBS-NN should not currently be given to women known, or suspected to be, pregnant, or to nursing mothers. Currently GBS-NN should only be administered to women of child-bearing potential if adequate contraceptive precautions are taken, accompanied by serum and/or urine pregnancy testing prior to vaccination and during follow up.

All study volunteers will be monitored for potential side effects of vaccination during the entire course of the study, as per the protocol, and adverse events must be appropriately followed up.

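### Section 15.4.2 specifies adverse event tables by SOC and PT only after splitting on investigator causality; it should also specify one for all TEAEs regardless of causality

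*Combined protocol and SAP*

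**What the plan says.** Section 15.4.2 sets out the adverse event displays for the primary endpoint.

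- **Overall summary.** "TEAEs will be described by relation to study vaccine" and by maximum intensity, for each treatment/dose group. The statistics are "number of TEAEs, number and percentage of volunteers with at least one TEAE (based on ITT" population). No breakdown by MedDRA term is mentioned.
- **Related TEAEs** (definite, probable or possible). These "will be summarised by MedDRA codes (SOC and PT) and treatment/dose group". A fallback applies: "In case of few vaccine related TEAEs (≤ 5 per study part for example), only a listing will be performed".
- **Not-related TEAEs.** Those with an "unlikely or unrelated relationship to study vaccine) will also be summarized by MedDRA codes".
- **Listings.** "Two distinct listings of TEAEs and NTEAEs will be presented by treatment/dose group, volunteer and MedDRA codes".
- **Reactogenicity**, handled apart from TEAEs. "Assessment results will be described according to treatment/dose group and visit".

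Section 14.2.2 says that the statistical output on causality is binary. Its definitions of definite, probable and possible all require the event to fit a recognised or anticipated reaction pattern for the vaccine; *unlikely* is defined by the lack of that fit. Section 6.3 states that the vaccine had not been given to humans before and that "the possibility of as yet unknown side effects should remain a consideration".

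**The concern.** The placebo group is there so that vaccine effects can be separated from background without relying on a judgement about each case. If every PT is first divided by the investigator's causality opinion, the tables show two partial contrasts for that PT and never the whole one.

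This matters most for a reaction nobody expects. Under section 14.2.2, such an event meets none of the three related categories, so *unlikely* is the highest category open to it and it is analysed as not related. A reader who looks for vaccine effects in the related table could miss it there. In a first-in-human vaccine whose primary objective is safety, the randomised comparison of each PT should be available without that filter.

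**Working it through.** The plan gives no figure to reproduce on this point. The check has three steps.

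**1. What each planned display shows**

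| Display in 15.4.2 | By group | By SOC/PT | All causalities together |
|---|---|---|---|
| Overall TEAE counts and percentages | yes | no | yes |
| Related TEAEs | yes | yes | no |
| Not-related TEAEs | yes, by the default in 15.1.1 | yes | no |
| TEAE listing | yes | coded, but woman by woman | yes |
| Reactogenicity | yes | not applicable | yes |

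No row is an incidence table with all three properties for coded events.

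**2. Can the two split tables be combined?**

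Suppose that a PT is reported for *a* women in the related table and *b* in the not-related table, out of *N*. The number with the PT at all lies between max(a, b), when the overlap is complete, and min(N, a + b), when there is none. Group sizes come from sections 12.2.1 and 12.2.2 (8 active per Part A cohort, up to 60 active per Part B regimen). The counts are assumed.

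- N = 60, a = 6, b = 6: 6 to 12 women, 10.0% to 20.0%.
- N = 60, a = 12, b = 9: 12 to 21 women, 20.0% to 35.0%.
- N = 8, a = 2, b = 2: 2 to 4 women, 25% to 50%.

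These limits presume that the tables count women. Section 15.4.2 does not say whether its SOC/PT tables count women or events; from event counts alone even these limits would not be available.

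The same uncertainty carries into the comparison. Take one Part B regimen (60) against pooled placebo (3 × 20 = 60), with 9 related and 6 not related on vaccine, and 3 and 2 on placebo (all assumed):

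| Comparison | Counts | Difference | Fisher p |
|---|---|---|---|
| Related only | 9 vs 3 | 10.0 points | 0.125 |
| Not related only | 6 vs 2 | 6.7 points | 0.27 |
| Any causality, no overlap in either arm | 15 vs 5 | 16.7 points | 0.026 |
| Any causality, full overlap in both arms | 9 vs 3 | 10.0 points | 0.125 |
| Any causality, full overlap on vaccine only | 9 vs 5 | 6.7 points | 0.39 |
| Any causality, full overlap on placebo only | 15 vs 3 | 20.0 points | 0.004 |

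The two tables are compatible with anything from a 6.7-point to a 20.0-point difference.

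**3. What the split does to power**

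Inputs: 3 × 60 = 180 active and 3 × 20 = 60 placebo, the Part B maximum. Assumed PT incidence: 30% vs 15%. Each affected woman is assumed to fall in one table only. Power is the sum of Bin(x; n₁, p₁) × Bin(y; n₂, p₂) over all (x, y) with a two-sided Fisher p ≤ 0.05.

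| Comparison | Rates | Power, 180 vs 60 | Power, 60 vs 60 |
|---|---|---|---|
| All causality | 30% vs 15% | 64% | 42% |
| Related only, half of events in both arms called related | 0.5 × 30 = 15% vs 0.5 × 15 = 7.5% | 29% | 17% |
| Related only, half of background and all of the excess called related | 0.5 × 15 + 15 = 22.5% vs 7.5% | 78% | 55% |

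With 25% vs 10% and half called related in both arms, 180 vs 60 gives 72% for all causality and 36% for related only (12.5% vs 5%).

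A further case follows from section 14.2.2. If half of the background but none of the vaccine excess is called related, the related table shows 7.5% vs 7.5%, no difference at all, and the contrast of 22.5% vs 7.5% appears in the not-related table.

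**The case against.** Several points on the other side are sound and set the limits of this one.

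- **More is planned than the two split tables.** A reader might infer that vaccine and placebo are never compared without a causality filter. The documents do not support that: overall TEAE incidence, reactogenicity and complete listings are all given by group. Many of the reactions expected in section 6.3 are local or flu-like and would be expected to show in the reactogenicity results.
- **Nothing is suppressed.** Not-related TEAEs are tabulated and listed too. An unexpected reaction might be missed in the related table, but it is not removed from the report, and any PT could be counted by hand from the listing.
- **The not-related table is by group.** Its sentence does not repeat the grouping, and a reader might take that as an omission. Section 15.1.1 makes treatment and dose group the default for all summaries.
- **A woman appearing in both tables is not an error.** Each table can be right for its own definition, and section 15.4.2 does not propose adding them. The overlap matters only because it prevents recovery of the all-causality count.
- **Splitting does not always dilute a difference.** If investigators attribute the excess well, the related table is the more sensitive display (78% against 64%). Section 15.4.2 describes adverse events and specifies no test per PT, so the power figures measure how clearly a difference would show, not the performance of a planned test.
- **Detail is left to the SAP.** Section 15 says so, and no separate list of tables is in the supplied text. The finding is therefore that the table is not specified here, not that it will never be produced. Even so, 15.4.2 is specific enough that an SAP following it would reproduce the gap.

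What remains is narrow: no incidence table is specified for individual SOCs and PTs regardless of causality, and the specified tables cannot supply it.

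**Conclusion.** The point holds for the incidence of individual SOCs and PTs in the supplied text, and no further. The loss of information is certain in kind, since the two tables give only a range for the all-causality count. Its consequence for detecting a difference is not fixed: it runs from a large loss (64% to 29%) to a gain (64% to 78%), depending on how blinded investigators attribute events, which the documents cannot predict. Those figures rest on the assumed incidences, on full Part B enrolment with the three regimens pooled, and on no woman falling in both tables. The case that most justifies a change is an unanticipated reaction, because the causality definitions themselves direct it away from the related table. This is worth correcting before the analysis; it does not call the design or the data into question.

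**What to change.** In section 15.4.2, make the main SOC/PT table one of all TEAEs regardless of relationship, by treatment/dose group including placebo. Give the number and percentage of women with at least one event, counting each woman once per SOC and once per PT. Keep the related and not-related tables as subsets of it.

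The events are already to be coded and listed, so no data collection, visit or test changes. The cost is one more output to produce and review.
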